SAE	serious adverse experience
SGLT	sodium-glucose cotransporter

PROTOCOL SYNOPSIS

TITLE	The effect of sodium-glucose cotransporter (SGLT) 2 inhibitor on cystine stone formation: A preliminary study
SPONSOR	[name]
FUNDING ORGANIZATION	
NUMBER OF SITES	1
RATIONALE	
Cystinuria is an inherited autosomal recessive disorder of the kidney that is the result of an inability to reabsorb cystine from the urine. Supersaturation of cystine in the urine produces crystals that precipitate and form stones in the kidney, which can be a cause of obstruction, infection, and chronic kidney disease. Cystine stones constitute a major health challenge for affected individuals with cystinuria because of the frequent recurrence of painful symptoms and the current absence of effective, patient-accepting treatment.
 
A mainstay of therapy is breaking or preventing the cystine bond on the molecular level such that cystine (which is formed from the joining of two cysteine amino acids and their corresponding sulfur atoms) cannot precipitate in the urine. It is hypothesized that a glucose molecule may be able to do this if introduced into the urine. SGLT-2 inhibitors are a class of drug that are FDA approved to treat diabetes mellitus (DM) and heart failure by inhibiting an enzyme in the kidney that allows for reabsorption of glucose from the urine. This effectively increases the concentration of glucose in the urine. Our hypothesis suggests that administration of this drug to patients with cystine will introduce sufficient glucose into the urine to prevent the formation of cystine stones. To date, there has been no published data on the effectiveness of this therapy for this indication, although the dosage and administration would be identical to that already approved by the FDA for the treatment of DM and heart failure.

STUDY DESIGN	This study will be a single center, proof of concept study designed to assess how daily 10 mg dapagliflozin affects formation of cystine in the urine in patients with cystinuria.
PRIMARY OBJECTIVE	Use mass spectrometry to determine the effect of SGLT-2 inhibitor therapy on quantitative sulfur as a surrogate for presence of cysteine in freshly voided urine in patients with cystinuria.
SECONDARY OBJECTIVES	None
NUMBER OF SUBJECTS	10
SUBJECT SELECTION	Inclusion Criteria: males and females age 18 or older; documented cystinuria on prior 24-hour urine collection and/or stone analysis;

SGLT2-02, [name]

CRITERIA	history of previous cystine kidney stones; and being able and willing to provide consent Exclusion Criteria: prior diagnosis of diabetes mellitus (type I or type II); current SGLT-2 inhibitor administration at the time of screening; SGLT-2 inhibitor administration within the last year prior to screening; vulnerable populations including incarceration status; anticipation of pregnancy during the study duration; unable to give informed consent; non-English primary language; pregnancy, lactation, or child- bearing age without birth control devices; and serious illness likely to cause death within the next 5 years.
TEST PRODUCT, DOSE, AND ROUTE OF ADMINISTRATION	Dapagliflozin 10 mg administered orally once daily for 4 weeks
CONTROL PRODUCT, DOSE AND ROUTE OF ADMINISTRATION	None
DURATION OF SUBJECT PARTICIPATION AND DURATION OF STUDY	Subjects will be on study for up to 6 weeks 
• Screening: 1 week to determine eligibility• Treatment: 4 weeks after the initial visit (Day 0)• Follow-up: 1 week after the last visit (Day 28)
CONCOMMITANT MEDICATIONS	Allowed: The participants will be allowed to continue any medications they are currently taking with the exception of those listed below under “prohibited”. Importantly, patients will be allowed to continue potassium citrate as this is an important mainstay of cystinuria treatment as discontinuation may lead to clinically significant cystine stone formation. Prohibited: Medications commonly used to treat diabetes, such as but not limited to insulin, metformin, and glipizides. These medications may interfere with the action of SGLT-2 inhibitors by altering the manner in which the body metabolizes and regulates glucose. Medications commonly used to treat cystinuria: thiola, penicillamine, alpha lipoic acid
EFFICACY EVALUATIONS	Efficacy in this study will be determined by utilizing mass spectrometry to analyze for the presence of sulfur in the urine before and after initiation of therapy with SGLT-2 inhibitor in our patients with cystinuria. Urinary cystine levels on 24-hour urine collection will also be measured.
PRIMARY ENDPOINT	Quantitative urinary sulfur via inductively coupled plasma optical emission spectroscopy (ICP-OES) in freshly voided urine

SGLT2-02, [name]

OTHER EVALUATIONS	
SAFETY EVALUATIONS	After participants are enrolled at 1 week during the treatment period, a study coordinator will contact each participant to check compliance, tolerability, and side effects with SGLT-2 inhibitor therapy. Any concern for a potential adverse event will be reviewed by the study investigators. Patient clinical care will continue as per the current standard for the duration of this study. Tolerability and side effects will be reviewed at each of the two clinic visits. All reported adverse events will be reviewed by the study investigators. Depending on the severity of the adverse event, the participant may be advised to stop SGLT-2 inhibitor therapy intake if it is determined that SGLT-2 inhibitor therapy is the cause. Most common AEs noted include male and female genital yeast infections, UTI, increased urination, discomfort with urination.
PLANNED INTERIM ANALYSES	When approximately 50% of patients have completed the study through Visit 2, an interim analysis for safety will be conducted. Serious adverse events will be monitored on an ongoing basis throughout the study.
STATISTICS Primary Analysis Plan	The primary efficacy endpoint will be assessed by comparing the qualitative and quantitative differences between the mass spectrometry output data between the participants' freshly voided urine at the initial visit and at the follow up visit after initiation of SGLT-2 inhibitor therapy, specifically examining the quantitative sulfur content between the two samples as a surrogate for cysteine in the urine.
Rationale for Number of Subjects	This is a preliminary proof of concept study designed to show only that administration of SGLT-2 inhibitor medications alter the excretion of cystine in the urine of patients with documented cystinuria. If initial analyses are promising, further investigation will be undertaken to draw further meaningful, statistical conclusions on the efficacy of this medication.

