Two primary factors known to affect the solubility of cystine include are cystine concentration and pH.⁷ Therefore, the current mainstays of therapy include aggressive hydration to 2.5 to 3 liters of fluid intake daily, lowering of dietary sodium intake, urinary alkalinization to pH >7.0, and thiol derivative medications to bind urinary cystine to reduce urinary cystine concentrations to less than 250 mg/l, the level above which cystine becomes insoluble in urine.⁸ Thiol derivatives in current use including D-penicillamine and alpha-mercaptopropionylglycione increase the solubility of cystine by forming more soluble mixed amino acid-disulfide products. However, these medications are difficult to tolerate due to their side effect profiles and, therefore, compliance is poor.⁹ Furthermore, the medications require regular monitoring of complete blood count, liver enzymes, and urinary protein excretion. In our own kidney stone clinic population, even when compliance is high, cystinuric patients taking D-penicillamine and alpha-mercaptopropionylglycione often continue to form recurrent cystine stones. It is not surprising that because cystinuria is a lifelong disease and current medical management is difficult to achieve and not very effective, these individuals have frequent stone recurrences and a higher risk of kidney loss compared to the average calcium oxalate stone former.¹⁰ Therefore, additional well-tolerated and effective medical therapies to treat cystinuria are desperately needed.

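### The primary endpoint switches between elemental sulfur and cystine-level signals; sulfur cannot directly show the proposed reaction, and the promised 24-hour cystine is on no schedule

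*Combined protocol and SAP*

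**What the plan says.** The synopsis entry for the primary endpoint reads "Quantitative urinary sulfur via inductively coupled plasma optical emission spectroscopy (ICP-OES) in freshly voided urine", and Section 9.2.1 names ICP-OES as the sulfur assay. The synopsis objective and Section 3.1 use mass spectrometry to measure sulfur as a stand-in for cysteine. The synopsis analysis plan does the same, "specifically examining the quantitative sulfur content between the two samples as a surrogate for cysteine in the urine". Section 5.1, which carries the title of primary efficacy endpoint, describes mass spectrometry signals for cystine, unbound cysteine and by-products of the reaction with glucose. Section 14.1 says the endpoint is also assessed by medical history and physical examination. Section 14.3 compares baseline with treatment mass spectrometry and names no analyte, unit or normalisation. No section says which direction of sulfur change would be a benefit.

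Under efficacy evaluations the synopsis adds: "Urinary cystine levels on 24-hour urine collection will also be measured". It gives no time points and lists no secondary objectives.

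Section 2 proposes that glucose breaks the disulfide bond in cystine. Section 1.1 says dapagliflozin increases urine volume, without a figure. Section 4.1 rules out a placebo.

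**The concern.** There are ten subjects, no control arm and one before-and-after comparison, so the study's conclusion rests on what is measured. If the sections disagree about the analyte, the primary result depends on which section is followed. If the analyte is elemental sulfur, a rise, a fall or no change could each occur with or without the Section 2 reaction. The decision on further research, which the synopsis and Section 14.5 tie to promising results, would then rest on a number that cannot support or refute the mechanism. A 24-hour cystine collection missed before treatment cannot be recovered afterwards.

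**Working it through.** The plan gives no figure on this point to reproduce. The checks below compare the passages and follow the sulfur.

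**1. Definitions side by side**

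| Place | What is measured | Method |
|---|---|---|
| Synopsis primary endpoint; assay in 9.2.1 | total sulfur | ICP-OES |
| Synopsis objective and analysis plan; 3.1 | sulfur, standing in for cysteine | mass spectrometry |
| 5.1 | cystine, free cysteine, by-products | mass spectrometry |
| 14.1 | adds history and physical examination | with mass spectrometry |
| 14.3 | not named | mass spectrometry |

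The first two rows share an analyte and differ in assay and label. The third measures something else.

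**2. Sulfur balance.** The synopsis describes "cystine (which is formed from the joining of two cysteine amino acids and their corresponding sulfur atoms", so one cystine (two sulfur atoms) gives two cysteines (one each). Inputs: 250 mg/L cystine as an anchor, from the Section 1 aim to "reduce urinary cystine concentrations to less than 250 mg/l, the level above which cystine becomes insoluble in urine"; molar masses from basic chemistry (cystine 240.30, sulfur 32.06).

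- Cystine: 250 / 240.30 = 1.040 mmol/L.
- At converted fraction f, cystine is 1.040(1 − f) and cysteine 2.081f mmol/L.
- Cystine-derived sulfur = [2 × 1.040(1 − f) + 2.081f] × 32.06 mg/L.

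| f | Cystine, mg/L | Cysteine, mmol/L | Sulfur, mg/L |
|---|---|---|---|
| 0% | 250 | 0 | 66.7 |
| 25% | 187.5 | 0.52 | 66.7 |
| 50% | 125 | 1.04 | 66.7 |
| 100% | 0 | 2.08 | 66.7 |

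**3. How sulfur can still move.** The amount of cystine reaching the sample may change. Suppose a fraction r = 10% had been retained in the kidney and none is now (assumed). Cystine-derived sulfur then goes from 66.7 to 66.7 / 0.90 = 74.1 mg/L, a rise of 11%, at any f. A change in cystine excretion also moves sulfur, in proportion to cystine's share of urinary sulfur, which the documents do not give.

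**4. Dilution.** With sulfur output unchanged, a proportional volume rise v lowers concentration by 1 − 1/(1 + v): 9% at v = 0.10, 17% at 0.20, 23% at 0.30. These sizes are assumed. A different assumption, 0.1 to 0.5 L/day added to 2.5 to 3 L/day (the Section 1 fluid intake target, used as a rough stand-in for output), gives 3% to 17%. Section 9.2.1 lists specific gravity but neither creatinine nor volume, and no adjustment is planned.

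**5. Schedule.** Sections 9.2.1, 10.1 and 10.2 and Appendix 1 contain no 24-hour collection. Urinalysis and mass spectrometry are separate items at both visits.

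**6. Behaviour of the replacement measure.** Creatinine-normalised cystine changes by the factor (1 − f)/(1 − r). At f = 25% it falls 25% with r = 0, and 17% with r = 10% (0.75/0.90; 208 mg/L on the 250 anchor). It rises if f is below r. The cysteine:cystine molar ratio, 2f/(1 − f), is 0.67 at f = 25% whatever the dilution or retention. It is undefined at full conversion and does not count cysteine bound in other compounds.

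**The case against.** The strongest reply is that the stated aim is narrower than the Section 2 mechanism. The synopsis says the study is meant to show only that the drug will "alter the excretion of cystine in the urine of patients with documented cystinuria", and sulfur can respond to that. This stands: for the excretion aim sulfur is non-specific, not blind. A reader might infer that sulfur cannot move at all, and the documents do not support that. The synopsis notes "Supersaturation of cystine in the urine produces crystals that precipitate and form stones in the kidney", so less precipitation would itself raise sulfur in the void.

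Second, the conflict may be smaller than it looks. ICP-OES sits under urinalysis, which is scheduled separately from mass spectrometry, so both assays may already be planned and only their ranking unclear. That reading is plausible. It remains uncertain because the synopsis and Section 3.1 tie mass spectrometry to sulfur, and nothing confirms that the scheduled assay separates cystine from cysteine.

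Third, Section 14 promises a detailed SAP before final analysis. A SAP could choose among the data collected and could adjust for specific gravity, imperfectly because urinary glucose may affect it. It could not supply a pre-treatment collection that was never made, and choosing the endpoint once data exist invites selection.

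Fourth, normalising to creatinine removes any benefit from dilution, although Section 1 treats hydration and cystine concentration as targets. That is fair, and is why un-normalised concentration should be reported as well.

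**Conclusion.** The point holds and should be settled before the first baseline sample. The primary endpoint is inconsistent, chiefly between elemental sulfur and species-level signals. The conservation result is exact: 66.7 mg/L sulfur at every conversion of 250 mg/L cystine. It rests only on the protocol's own description of cystine and on basic chemistry. The absence of the 24-hour cystine from the schedule is a matter of record.

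Three stronger readings are not supported.

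- A reader might count four rival endpoints. Two share sulfur as the analyte, and the history-and-examination sentence stands alone under data sets analysed, with nothing matching it in Section 14.3.
- A reader might conclude that spot sulfur will fall on treatment. Section 1.1 gives a direction for urine volume but no size, its quantified glucose data come from type 2 diabetes, which is excluded here, and a single void need not follow daily volume. It may fall, by 9% to 23% under the assumed 10% to 30% rise.
- A reader might infer that dilution would outweigh a real change in cystine excretion. That comparison needs cystine's share of urinary sulfur and the size of the volume rise, and the documents give neither.

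**What to change.** Before any sample is taken, use one analyte, assay, unit and normalisation as primary in the synopsis and Sections 3.1, 5.1, 9.2.1, 14.1 and 14.3, and make it specific to cystine.

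- If the scheduled mass spectrometry is confirmed to resolve cystine and cysteine: within-subject change from Visit 1 to Visit 2 in fresh-void cystine, as Section 5.1 already describes, normalised to creatinine in the same void. If it does not: the 24-hour cystine already promised, in mg/day.
- Report un-normalised cystine concentration and the cysteine:cystine ratio alongside. State the expected direction, and note that relief of retention in the kidney could partly mask or reverse a fall in cystine.
- Make ICP-OES sulfur exploratory, and remove history and physical examination from the primary endpoint in Section 14.1.
- Add the 24-hour cystine to Sections 10.1 and 10.2 and Appendix 1, with the baseline collection after consent and before treatment begins. The synopsis period "Screening: 1 week to determine eligibility" can hold it if consent is taken at its start. Section 10.1 now places consent and the prescription at the same visit.
- Reconcile Section 4.1, which describes subjects as untreated apart from potassium citrate, with Section 7, which has them stop thiol drugs without saying when relative to the baseline void. Report the medication dates captured under Section 9.1.1 beside the endpoint.

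The cost is protocol wording, one urine creatinine per visit (not in the Section 9.2.1 panel), scheduling of the 24-hour collections, and confirmation of the assay, which is the main uncertainty.

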5 CRITERIA FOR EVALUATION

5.1 Primary Efficacy Endpoint

The primary endpoint will be assessed via analysis using mass spectrometry of freshly voided urine and examining the resultant signals which signify the presence or absence of cystine as well as unbound cysteine amino acids and other reduction byproducts through the reaction with glucose. These will be assessed after 4 weeks of treatment with daily oral dapagliflozin 10 mg.

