8.2 Blinding

This is a nonblinded proof of concept study.

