14.3 Analysis of Primary Endpoint

The primary endpoint will be analyzed through quantitative comparison between the baseline urine mass spectrometry analysis and the treatment urine mass spectrometry analysis.

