16 ADMINISTRATIVE, ETHICAL, REGULATORY CONSIDERATIONS

The study will be conducted according to the Declaration of Helsinki, Protection of Human Volunteers (21 CFR 50), Institutional Review Boards (21 CFR 56), and Obligations of Clinical Investigators (21 CFR 312).

To maintain confidentiality, all laboratory specimens, evaluation forms, reports and other records will be identified by a coded number and initials only. All study records will be kept in a locked file cabinet and code sheets linking a patient's name to a patient identification number will be stored separately in another locked file cabinet. Clinical information will not be released without written permission of the subject, except as necessary for monitoring by the FDA. The Investigator must also comply with all applicable privacy regulations (e.g., Health Insurance Portability and Accountability Act of 1996, EU Data Protection Directive 95/46/EC).

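### The primary assessment includes a qualitative reading of spectra, and the protocol neither masks the reader to visit nor fixes a reading rule; the numeric sulfur value is much less exposed.

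*Combined protocol and SAP*

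**What the plan says.** The primary assessment is described in several places, and not in the same way.

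- **Synopsis, Primary Endpoint:** "Quantitative urinary sulfur via inductively coupled plasma optical emission spectroscopy (ICP-OES) in freshly voided urine".
- **Synopsis, Primary Analysis Plan:** "comparing the qualitative and quantitative differences between the mass spectrometry output data" at the two visits. The same sentence goes on to say "specifically examining the quantitative sulfur content between the two samples as a surrogate for cysteine in the urine".
- **Section 5.1:** "examining the resultant signals which signify the presence or absence of cystine as well as unbound cysteine amino acids", together with other by-products of the reaction with glucose, which are not named.
- **Section 14.1:** adds medical history and physical examination to the mass spectrometry data.
- **Section 14.3:** "The primary endpoint will be analyzed through quantitative comparison between the baseline urine mass spectrometry analysis" and its on-treatment counterpart. No qualitative reading is mentioned.

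On masking, section 8.2 says only "This is a nonblinded proof of concept study". Section 4.1 rules out a placebo. Section 10.1 (item 11) has the baseline analysis obtained at Visit 1, and section 10.2 (item 6) has the treatment analysis obtained at Visit 2. Section 16 says that "all laboratory specimens, evaluation forms, reports and other records will be identified by a coded number and initials only", and gives confidentiality as the purpose. No section names the reader, a peak list, an integration rule or a cut-off for calling cystine present.

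**The concern.** In a one-arm study the treatment cannot be masked, but the reading of the laboratory output can. Deciding whether a signal counts as present, where a peak begins and ends, or whether an unnamed by-product has appeared involves judgement. If the person judging knows which spectrum comes from the treated visit, the hoped-for answer is known too.

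The contrast is before versus after within each subject, so no control arm would show the same reader drift and allow it to be subtracted. Any expectation effect goes into the apparent drug effect. Sections 14 and 14.5 add to this. The detailed SAP is due only before analysis of the final data, so reading rules could be written after spectra have been seen. Whether to go on to a powered study depends on results that look promising, a term without a stated criterion.

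**Working it through.** The documents state no alpha, test, effect size or SD for the 10 subjects, so there is no planned figure to reproduce. The check is mainly textual.

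**1. Is a judged reading part of the primary assessment?** Yes, by the synopsis analysis plan and section 5.1. It is not the whole of it. The synopsis endpoint, the objective in section 3.1 and section 14.3 are quantitative, and section 9.2.1 lists only ICP-OES sulfur beyond routine urinalysis.

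**2. Is the reader masked?** No section says so. Section 8.2 declares the study nonblinded and makes no exception for the laboratory. Section 16 coding puts initials on specimens, which allows the two samples of a subject to be paired. It does not say that visit or date is shown or hidden. If urine is run when collected, as sections 10.1 and 10.2 read, the run date reveals the visit whatever the label says.

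**3. Can the sample reveal itself?** Probably in part. Section 2 says that the drug sharply raises urinary glucose, and section 5.1 looks for products of the reaction with glucose.

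**4. Illustration of size, for the qualitative component only.** The tests and bias rates are assumptions.

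*Present/absent calls in 10 pairs, exact two-sided sign (McNemar) test at 0.05.* Pairs with the same call at both visits drop out. With d discordant pairs all in one direction, p = 2 × (1/2)^d:

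- d = 5: 2/32 = 0.0625
- d = 6: 2/64 = 0.031

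Six favourable calls with none the other way would therefore be enough. Suppose no drug effect, a random call of probability e in each direction per pair, and an added probability b of a favourable call driven by expectation. Each pair is then favourable with probability e + b, unfavourable with probability e, and otherwise unchanged. Summing the trinomial probabilities of all favourable outcomes with p ≤ 0.05 gives:

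| b | e = 0.05 | e = 0.10 |
|---|---|---|
| 0 | 0.0% | 0.0% |
| 0.2 | 1.5% | 2.7% |
| 0.3 | 7.2% | 9.0% |
| 0.5 | 36.4% | 33.0% |

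*Forced call of which visit looks better, no ties, 10 pairs.* Nine of 10 are needed: two-sided p = 2 × 11/1024 = 0.021. With probability q of a call favouring Visit 2, P(at least 9) = 10q⁹(1 − q) + q¹⁰:

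- q = 0.5: 1.1%
- q = 0.6: 4.6%
- q = 0.7: 14.9%
- q = 0.8: 37.6%

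The first model is closer to section 5.1, because that section speaks of presence or absence and unchanged pairs carry no information. Neither model describes the ICP-OES sulfur value.

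**The case against.** The strongest objection is that the endpoint is really a number. The synopsis sentence narrows to quantitative sulfur, and the objective, the named endpoint and section 14.3 agree. An instrument readout of sulfur leaves little room for expectation. This stands, and it limits the point to the qualitative component. It does not remove the point, because the synopsis analysis plan and section 5.1 keep that component inside the primary assessment.

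A reader might infer three stronger things that the documents do not support.

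- *That staff who know which sample is on drug read the spectra.* No section says who reads them or what they know. The supportable statement is that nothing prevents it and that the visit-by-visit schedule makes it likely.
- *That masking is free and complete.* It needs a link file and delayed reading, and glucose or its by-products may still reveal the visit.
- *That the percentages above are this trial's false-positive risk.* The protocol names no test and no threshold, defines no call of which visit is better, and leaves statistical conclusions to later work. The bias rates have no source in the documents.

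It can also be said that the later SAP may contain the reading rules. It may, but it cannot mask laboratory work already done, and section 14 does not require it before Visit 2 spectra are seen.

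**Conclusion.** The point holds in a limited form. A qualitative reading of signals sits within the primary assessment of an uncontrolled, nonblinded before-after study, with no masking of the reader and no reading rule. Expectation could therefore influence that component. The quantitative sulfur value is much less exposed, and if the sections were reconciled to sulfur alone the point would largely fall away.

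The size cannot be derived from the documents. Under the assumed present/absent model, the chance of a spurious favourable result is about 1.5-2.7% when expectation drives 20% of pairs, 7-9% at 30%, and 33-36% at 50%. The effect is small for mild bias and serious only if bias is strong. The case for acting rests on the low cost of the remedy and the lack of a control arm, not on these percentages.

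**What to change.** In sections 8.2 and 9.2.1, state that treatment is open-label but that spectra are read masked to subject and visit:

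- Give each aliquot a random code carrying no subject, date or visit. If urine must be run fresh, recode the exported spectrum files in the same way.
- Fix the peak windows, integration rules and present/absent cut-off before the first Visit 2 spectrum, and name the by-products sought.
- Read all files together after the last Visit 2. Read cystine and cysteine before any glucose-related signal, and keep the urinalysis glucose result from the reader.
- Open the link only after the readings are locked.

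Alternatively, confine the primary endpoint to quantitative sulfur, move the signal reading to an exploratory role, and reconcile the synopsis endpoint and analysis plan with sections 5.1, 14.1 and 14.3. This has a scientific price. Breaking the disulfide bond does not change the number of sulfur atoms, so a sulfur total alone cannot show the conversion hypothesised in section 2.

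The cost of masking is a link file held by someone other than the reader, slightly later readings, and no visit-by-visit results for the investigators. It needs no extra staff or subject procedure. Masking may remain incomplete for the glucose by-products, and the report should say so.

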1.1 Overview of Clinical Studies

Sodium-glucose cotransporter 2 (SGLT2), expressed in the proximal renal tubules, is responsible for the majority of the reabsorption of filtered glucose from the tubular lumen. Dapagliflozin is an inhibitor of SGLT2. By inhibiting SGLT2, dapagliflozin reduces reabsorption of filtered glucose and lowers the renal threshold for glucose, and thereby increases urinary glucose excretion. Dapagliflozin also reduces sodium reabsorption and increases the delivery of sodium to the distal tubule. This may influence several physiological functions including, but not restricted to, lowering both pre-and afterload of the heart and downregulation of sympathetic activity.

SGLT2-02, [name]

Increases in the amount of glucose excreted in the urine were observed in healthy subjects and in patients with type 2 diabetes mellitus following the administration of dapagliflozin. Dapagliflozin doses of 5 or 10 mg per day in patients with type 2 diabetes mellitus for 12 weeks resulted in excretion of approximately 70 grams of glucose in the urine per day at Week 12. A near maximum glucose excretion was observed at the dapagliflozin daily dose of 20 mg. This urinary glucose excretion with dapagliflozin also results in increases in urinary volume. After discontinuation of dapagliflozin, on average, the elevation in urinary glucose excretion approaches baseline by about 3 days for the 10 mg dose.

Following oral administration of dapagliflozin, the maximum plasma concentration (Cmax) is usually attained within 2 hours under fasting state. The Cmax and AUC values increase dose proportionally with increase in dapagliflozin dose in the therapeutic dose range. The absolute oral bioavailability of dapagliflozin following the administration of a 10 mg dose is 78%. Administration of dapagliflozin with a high-fat meal decreases its Cmax by up to 50% and prolongs Tmax by approximately 1 hour, but does not alter AUC as compared with the fasted state. These changes are not considered to be clinically meaningful and dapagliflozin can be administered with or without food.

Overview of Clinical Studies of FARXIGA for Type 2 Diabetes

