3 STUDY OBJECTIVES

3.1 Primary Objective

The primary objective of this study is to use mass spectrometry to determine the effect of SGLT-2 inhibitor therapy on quantitative sulfur as a surrogate of cysteine in freshly voided urine in patients with cystinuria

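### Spot-void sulfur with no unit or index cannot by itself separate dilution from a change in excretion, and the promised 24-hour cystine is never scheduled

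*Combined protocol and SAP*

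**What the plan says.** The synopsis gives the primary endpoint as "Quantitative urinary sulfur via inductively coupled plasma optical emission spectroscopy (ICP-OES) in freshly voided urine". Section 3.1 describes the target as "quantitative sulfur as a surrogate of cysteine in freshly voided urine in patients with cystinuria". The synopsis analysis plan contrasts the Visit 1 and Visit 2 samples, "specifically examining the quantitative sulfur content between the two samples as a surrogate for cysteine in the urine", and Section 14.3 says no more than that baseline and treatment results will be compared quantitatively.

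On purpose, the synopsis rationale for the number of subjects says the study is to show that the drug class will "alter the excretion of cystine in the urine of patients with documented cystinuria".

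On the drug, Section 1.1 states: "This urinary glucose excretion with dapagliflozin also results in increases in urinary volume".

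On what is measured, Section 9.2.1 lists a routine urinalysis, including specific gravity and glucose, and an ICP-OES sulfur sample. Sections 10.1 and 10.2 and Appendix 1 list urinalysis and the spectrometry sample at each visit. Urine creatinine, void volume, collection interval and time of day appear in none of them.

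Under Efficacy Evaluations, the synopsis also promises cystine on a 24-hour urine collection. The only other references to 24-hour urine, in the inclusion criteria of the synopsis and Section 6.2, concern past collections used for eligibility.

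**The concern.** A spot-urine value can be read as excretion only if it is tied to a denominator: creatinine, volume or elapsed time. Here the denominator is missing and, on the protocol's own account, the drug moves it. If sulfur is reported as a concentration, extra water lowers it with excretion unchanged, or hides a rise in excretion. If it is reported as an amount per void, it depends on how long the subject waited before voiding.

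The missing placebo arm is a separate limitation (drift in time and hydration) and is not the cause. A placebo contrast would still carry the drug's own effect on volume.

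The 24-hour cystine collection would address excretion directly, but staff who follow the visit lists and Appendix 1 would not obtain it. Section 14 defers detail to an SAP still to be written. An SAP can define a unit; it cannot supply creatinine, volume or a timed collection that nobody took.

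**Working it through.** **Plan's own figure.** The only design figure is the sample size of ten (Section 14.5). It has no stated effect size, SD, alpha or power, so there is nothing to reproduce.

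**Inputs.** The documents give no urine volumes. The nearest figure, in Section 1, is an intake target: "aggressive hydration to 2.5 to 3 liters of fluid intake daily". Baseline urine volume V and the drug-related rise d are therefore assumptions, and daily averages are only a rough guide to a single void.

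**Step 1: dilution with excretion unchanged.** Concentration ratio (Visit 2/Visit 1) D = V/(V + d).

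- V = 3.0, d = 0.2 L/day: 3.0/3.2 = 0.9375, a fall of about 6%.
- V = 2.5, d = 0.5: 2.5/3.0 = 0.833, a fall of about 17%.
- V = 2.0, d = 0.5: 2.0/2.5 = 0.80, a fall of 20%.

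**Step 2: rise in excretion fully hidden.** This is 1/D − 1. For the same three cases it is 6.7%, 20% and 25%.

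**Step 3: whether the direction of change can be read from the raw ratio.** True excretion ratio = observed ratio/D.

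- With V = 1.5 and d = 0.5, D = 1.5/2.0 = 0.75. An observed 0.78 then gives 0.78/0.75 = 1.04, a rise in excretion behind a 22% fall in concentration.
- If the Visit 2 void happens to be 25% more concentrated (assumed), an observed 1.10 gives 1.10/1.25 = 0.88, a fall behind an apparent rise.

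So no cut-off on the raw ratio reliably gives the direction.

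**Step 4: amount per void.** At a constant excretion rate, a void 3 hours after the last holds 3/2 = 1.5 times the sulfur of one after 2 hours (assumed intervals).

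**Step 5: what an index does.** Sulfur concentration is sulfur excreted/volume, and creatinine concentration is creatinine excreted/volume. In their quotient the volume cancels. With stable creatinine excretion and unchanged sulfur excretion, the expected Visit 2/Visit 1 ratio is 1.00 whatever the dilution.

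**Step 6: treatment timing.** The synopsis and Sections 4.1, 8.4, 8.4.1 and 8.4.2 say 4 weeks; Sections 5.2 and 8.1 say one week. Section 1.1 says that after stopping, "the elevation in urinary glucose excretion approaches baseline by about 3 days for the 10 mg dose". Taking a Day 0 start as an assumption, the one-week wording would place Visit 2 about 28 − 7 = 21 days after treatment ended. Whether the Day 28 urine is an on-treatment sample depends on which statement applies.

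**The case against.** The strongest reply is that excretion is not the only target the text supports. It is named in one sentence, the rationale for the number of subjects. The primary objective concerns sulfur in fresh urine, and the synopsis and Section 4.1 speak of cystine formation. Section 1 ties solubility to concentration; thiol drugs aim to "reduce urinary cystine concentrations to less than 250 mg/l, the level above which cystine becomes insoluble in urine". A dilution-driven fall in concentration could therefore matter clinically. This stands, and it is why raw concentration should be kept and labelled as such.

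Second, indexing does not turn sulfur into cystine. Sulfur/creatinine is still total sulfur, and splitting cystine into two cysteines leaves the same sulfur atoms. This also stands: only the 24-hour cystine addresses cystine excretion directly.

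Third, Section 5.1 mentions cystine and cysteine signals, whose ratio within one sample is unaffected by dilution. This limits the point to the sulfur measure, although no quantification of those signals is specified.

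Fourth, specific gravity is collected. It offers only a rough check: no adjustment is planned, and the glucose that the drug adds itself raises it.

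Finally, this is an unpowered ten-subject proof of concept. That bears on precision; the gap here is in what is measured.

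**Conclusion.** The point holds in a limited form and should be fixed before enrolment. Unindexed spot sulfur cannot by itself separate dilution, or void size and timing, from changed excretion. Under the assumed volumes, dilution alone lowers concentration by about 6% to 20%; these are illustrations, not document values. The omission of the 24-hour cystine from the laboratory section, visit lists, statistics section and Appendix 1 is a separate inconsistency and rests on no assumption.

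Three stronger readings are tempting, and the documents do not support them:

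- A reader might infer that the trial can show nothing useful. The wording also allows a concentration target, and the Section 5.1 signals could give a dilution-free ratio.
- A reader might use the 6% to 20% range as a decision rule, taking larger falls as true falls in excretion and any rise as a true rise. Spot voids can vary more, and in either direction, so that rule fails.
- A reader might quote a false-positive rate. The plan names no test and gives no variability, so none can be claimed.

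**What to change.** 1. Measure creatinine in the same Visit 1 and Visit 2 urine, state the sulfur unit, and report sulfur/creatinine as a paired log-ratio (Visit 2/Visit 1) with a 95% CI. Report raw concentration alongside, each labelled as what it is.
2. Add the 24-hour collection to Sections 9.2, 10.1, 10.2 and Appendix 1: once after consent and before the first dose, and once while still on treatment. Record volume and give cystine in mg/day and mg/L. If it will not be done, delete it from the synopsis and limit the conclusion to urinary sulfur. The past collection in Section 6.2 cannot serve as baseline: it has no time limit, and stone analysis can replace it.
3. Take both spot samples at a similar time of day and record the void time.
4. State that indexed total sulfur corrects for dilution only, is not specific to cystine and cannot show disulfide cleavage. If the Section 5.1 cystine and cysteine signals are quantified, report their within-sample ratio.
5. Reconcile the 4-week and one-week treatment statements before timing the on-treatment collection.

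**Cost.** About 20 creatinine assays (10 subjects × 2 visits) on urine already collected, and participant effort for about 20 collections already promised. Consent, baseline urine and prescription all fall on Day 0, and Section 9 allows no study activity before consent. The baseline collection therefore needs consent during the one-week screening period or an extra contact. The creatinine index assumes stable creatinine excretion between the visits.
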